#### **14.2 Approvals**

The study protocol, informed consent form, participant information sheet and any proposed advertising material will be submitted to an appropriate Research Ethics Committee (REC) for written approval. Any subsequent updates to these documents will also be sent to the REC for their approval prior to use in the study.

#### **14.3 Study Reports**

Annual progress reports and a final report at conclusion of the study will be submitted to the Research Ethics Committee within the required timelines.

#### **14.4 Participant Confidentiality**

The study researchers will ensure that the participants' anonymity is maintained. The participants will be identified by a study participant number on the P1vital® ePRO and i-spero® systems. Only the participant consent form and contact details form will include the participant's name, and these will be stored separately from other study data. All documents will be stored securely and only accessible by study staff and authorised personnel. The study will comply with the UK Data Protection Act 2018 which requires data to be anonymised as soon as it is practical to do so.

### **15.0 Expenses, Benefits**

Participants will not be reimbursed financially for doing the intervention, for the following reasons:

- All participants may potentially benefit clinically, as participants in both arms will receive the intervention (either immediately or after a delay of 4 weeks).
- We wish for uptake of the intervention to be motivated by clinical benefit (a reduction in intrusive trauma memories) rather than financial benefit, to indicate naturalistic uptake in preparation for roll-out of the intervention.
- No travel expenses are incurred, as the study is run entirely remotely using digital platforms that participants can access from their own home or another preferred location.

However, as an incentive to complete follow-up measures, participants will be offered a £10 online voucher at the end of the study.

### **16.0 Financial Aspects**

The study is funded by Wellcome Trust discretionary project grant award (223016/Z/21/Z) in mental health.

### **17.0 Use of Information and Publication**

All information, including but not limited to scientific research data, generated as a result of this study, are considered confidential and remain the sole property of P1vital and its

**Confidential**

P1V\_GAINS\_IN01 Study Protocol

academic and pharmaceutical company collaborators. The results of the primary, secondary and tertiary analysis will be reported in a Study Report generated by P1vital Products Ltd (or delegate).

Any anonymised data collected from the intervention use after participants have completed the trial, will only be used to optimise the intervention, and will not be considered research data.

Study results will be also published in peer-reviewed journals and presented at scientific conferences. Study subject identifiers will not be used in any publications.

## APPENDIX 1: TIME AND EVENT SCHEDULE

Virtual Visit Name	Items	Screening	Run-in week	Baseline	Week 1	Week 2	Week 3	Week 4	Week 5	Week 6	Week 7	Week 8	Follow Up
Day				D1	D1 to D7	D8 to D14	D15 to D21	D22 to D28	D29 to D35	D36 to D42	D43 to D49	D50 to D56	D57 to D70
Visit Window		D-35	D-35 to D-21	D-28 to D1					D29 + 7days (Del)	+7 days (Del)	+7 days (Del)	+7 days (Del)	+7 days (Del)
Procedures and Assessment Tasks													
Participant information sheet		x											
Eligibility questionnaire	9	x											
Consent form		x											
Inclusion/Exclusion Criteria		x											
Contact details		x											
Intrusive memory diary (daily)			xxxxxx					xxxxxx				xxxxx x (Del)	
Intrusive memory ratings	10		x 					x 				x 	
Randomisation				x									
Credibility/Expectancy Questionnaire	6			x									
Demographics	10			x									
Health background	6			x									
Checklist of traumatic events	4			x									
Perceived threat to self/other	2			x									
Peritraumatic Distress Inventory	13			x									
Impact of Event Scale – Revised (IES-R)	22			x				x 				x 	
PTSD Checklist for DSM-5 (PCL-5)	4			x				x 				x 	

**Confidential**

**P1V\_GAINS\_IN01 Study Protocol**

[figure not shown]
Generalized Anxiety Disorder (GAD-2)	2			x				x 					x 	
Patient Health Questionnaire (PHQ-2)	2			x				x 					x 	
Sleep Condition Indicator (SCI-08)	8			x				x 					x 	
Psychological Outcome Profiles Questionnaire (PSYCHLOPS)	4			x				x 					x 	
World Health Organization Disability Assessment Schedule (WHODAS) 2.0	12			x				x 					x 	
EQ- 5D-5L (5-level EuroQol 5D)	5			x				x 					x 	
Sickness absence	1			x				x 					x 	
Scale of Work Engagement and Burnout (SWEBO)	18			x				x 					x 	
Support from managers And friend/family	2			x										
Intention To Leave Job	3			x				x 					x 	
Changes to health and work	9							x 					x 	
Intervention: List of intrusive memories (hotspots)							x..x(Imm)					x..x(Del)		
Intervention: Distress rating (x3)	1						x..x(Imm)					x..x(Del)		
Intervention: Reactivation Vividness rating	1						x..x(Imm)					x..x(Del)		
Intervention: Playing the computer game Tetris (at least for 20 minutes)							x..x(Imm)					x..x(Del)		
Intervention: mental rotating rating	1						x..x(Imm)					x..x(Del)		

**Confidential**

P1V\_GAINS\_IN01 Study Protocol

Record of intrusive memories (daily)					x..x(Imm)				x..x(Del)				
Feedback questionnaire	11							x(Imm)				x(Del)	
Qualitative interview (Optional)									$x^3$				$x^3$
Note: measures in bold are in i-spero; measures not in bold are in ePRO; Del = delayed-intervention arm, Imm = immediate-intervention arm, X = all participants (immediate and delayed intervention arms)													

1. To be completed by participants at the end of the week (7th day)

2. Participant for both arms will have a +7 days window to complete week 4 and week 8 outcome measures.

3. Optional qualitative interview for immediate and delayed intervention arm can be completed within 14 days of day 29 and 57 respectively.

4. Feedback questionnaire can be completed within 14 days of days 28 and 56 for delayed and immediate intervention arm participants respectively.

													

## Changes from protocol

The table below details changes to the planned analyses in the SAP compared to the protocol which after discussion with the TMG are not considered to require a protocol amendment.

Protocol version and section	Protocol text	SAP version and section	SAP text	Justification

## Amendments to versions

Version	Date	Change/comment	Statistician
3.0	23Jun2022	Adding subsection 5.1.2 which includes the reason for including primary outcome compliance measure	[name]
2.0	20Jun2022	Table 3 (primary outcome compliance measure) added to section 5.1	[name]

## Abbreviations

Abbreviation	Description
AE	Adverse Event
BF	Bayes Factor
COVID-19	Coronavirus Disease 2019
DMC	Data Monitoring Committee
DSM-5	Diagnostic and Statistical Manual of Mental Disorders, 5th Edition
GAD-2	Generalised Anxiety Disorder – 2-item questionnaire
GCP	Good Clinical Practice
GP	General Practitioner
ePRO	Electronic Patient Reported Outcomes
EQ-5D-5L	5-level EQ-5D
ICF	Informed Consent Form
ICU	Intensive Care Unit
IES-R	Impact of Event Scale-Revised
IMs	Intrusive Memories
NHS	National Health Service
PCL-5	PTSD Checklist for DSM-5
PHQ-2	Patient Health Questionnaire – 2-item version
PI	Principal Investigator
PIS	Participant Information Sheet
PD	Probability of Direction
PSYCHLOPS	Psychological Outcome Profiles Questionnaire
PTSD	Post-traumatic Stress Disorder
REC	Research Ethics Committee
SAP	Statistical Analysis Plan

SCI	Sleep Condition Indicator
SWEBO	Scale of Work Engagement and Burnout
TMG	Trial Management Group
TSC	Trial Steering Committee
WHO	World Health Organization
WHODAS	World Health Organization Disability Assessment Schedule

# 1. Introduction

This document seeks to follow the template and guidelines proposed by Gamble et al. (2017) when analysing and reporting the main results from the current study titled “A randomised optimisation study of a brief digital imagery-competing task intervention to support NHS ICU staff experiencing intrusive memories of traumatic events from working in the COVID-19 pandemic”, which is shorted as “A brief GAmesplay Intervention for NHS ICU Staff affected by COVID-19 trauma (GAINS Study)”. These analyses will explore the efficacy and safety of a brief digital imagery-competing task intervention in comparison with usual care and will be included in the clinical study report, to inform a future definitive clinical trial design.

The purpose of the plan is to:

- Ensure that the analysis is appropriate for the aims of the trial, reflects good statistical practice, and that interpretation of a priori and post hoc analyses respectively is appropriate.
- Explain in detail how the data will be handled and analysed to enable others to perform or replicate these analyses.

Bayesian and frequentist analyses were proposed for statistical inference in this study. The Bayesian approach will be used throughout data collection to inform on study design and the details can be found in a separate file named “*P1V\_GAINS\_IN01 Optimisation SAP.pdf*”. The present document (the “D-SAP”) will present the details for all frequentist analysis in line with the analysis specified in study protocol.

Additional exploratory or auxiliary analyses of data not specified in the protocol may be included in this analysis plan. This analysis plan will be made available in a public platform before the trial database is locked for the final analysis. Additional analyses suggested by reviewers or editors will be performed if considered appropriate. This will be documented in a file note. Amendments to the statistical analysis plan will be described and justified in the final report of the trial and where appropriate in publications arising from the analysis.

Other health economic and qualitative analysis plans are beyond the scope of this document. Note the quantitative part of the Intervention Feedback questionnaire will be analysed (See Section 5 for details).

## **1.1 Background and rationale**

Intensive care unit (ICU) staff are frequently exposed to traumatic events at work (e.g., witnessing patients die), amplified by the COVID-19 pandemic. A significant proportion experience intrusive memories (or “flashbacks”) of these events that pop suddenly into mind: these imagery-based memories can disrupt functioning and contribute to posttraumatic stress disorder. Previous research has shown that a brief behavioural intervention can reduce the number of intrusive memories after a traumatic event.

In this study we aim to optimise a brief digital intervention to help reduce the number of intrusive memories (primary outcome) experienced by ICU staff.

We will explore if it can improve clinical, work functioning and wellbeing measures (secondary outcomes).

We will recruit up to 150 staff with intrusive memories of events experienced whilst working in an ICU during the COVID-19 pandemic.

## **1.2 Objectives**

The main objective is to optimise a brief digital intervention to help reduce the number of intrusive memories experienced by staff who worked in an ICU during the pandemic (primary outcome). The process is that interim analyses for the primary outcome will be used to guide study optimisation and assess evidence for early stopping of the trial (detailed in the *P1V GAINS IN01 Optimisation SAP*). This means that the intervention can evolve and improve over the course of the trial and will be used to inform the next trial.

Once the trial has concluded, a standard analysis will be conducted as described in this SAP (of the type that may be used in the next trial).

The primary objective of this trial is to determine if immediate access to the intervention plus symptom monitoring for 4 weeks (immediate intervention arm), compared to usual care for 4 weeks (delayed intervention arm), can reduce the number of intrusive memories in week 4 (i.e. between-groups comparison). See Section 2.1 for details of the trial design.

The secondary objectives of this trial are:

- To determine if access to the intervention plus symptom monitoring for 4 weeks can reduce the number of intrusive memories from run-in week (pre-intervention) to week 4 (post intervention; within-group comparison in the immediate intervention arm) and from week 4 (pre intervention) to week 8 (post intervention; within-group comparison in the delayed intervention arm)
- To determine if immediate access to the intervention plus symptom monitoring for 4 weeks (immediate intervention arm), compared to usual care for 4 weeks (delayed intervention arm), can reduce intrusive memory ratings of distress and disruption to concentration/functioning; symptoms of post-traumatic stress, anxiety, depression and insomnia; sickness absence; burnout; intention to leave job; and improve work engagement, functioning and quality of life at 4 weeks (i.e. between-groups comparison).
- To determine if access to the intervention plus symptom monitoring for 4 weeks can reduce intrusive memory ratings of distress and disruption to concentration/functioning; symptoms of post-traumatic stress, anxiety, depression and insomnia; sickness absence; burnout; intention to leave job; and improve work engagement, functioning and quality of life from baseline (pre intervention) to 4 and 8 weeks (post intervention; within-group comparison in the immediate intervention arm) and from 4 weeks (pre intervention) to 8 weeks (post intervention; within-group comparison in the delayed intervention arm).

The tertiary objectives of the trial are:

- To assess new stressful/traumatic events, new treatments, changes to work.
- To obtain feasibility data to improve the intervention implementation.
- To assess the acceptability and perceived value of the intervention from participants to optimise the intervention implementation.
- To assess the guidance given by the expert researchers to participants to explain how to use the intervention, in order to identify ways to train non-

expert researchers to give guidance (assessed qualitatively: not included in this SAP).

- To assess the guidance given by both expert and non-expert researchers to identify ways to digitise such guidance to establish a fully self-guided version of the intervention (assessed qualitatively: not included in this SAP).

## 2. Study methods

### 2.1 Trial design

The study is a two arm, parallel group, randomised optimisation study of a brief digital imagery-competing task intervention to support NHS ICU staff experiencing intrusive memories of traumatic events from working in the COVID-19 pandemic.

Participants will be randomised to one of two study arms:

- **Immediate intervention arm:** immediate access to the brief digital imagery-competing task intervention plus symptom monitoring for 4 weeks.
- **Delayed intervention arm:** usual care for 4 weeks followed by access to the intervention plus symptom monitoring for 4 weeks

The study is divided into a 1–5-week screening period, randomisation into an immediate intervention or delayed intervention arm using a 1:1 overall ratio, 8 week in-study period, followed by two weeks optional qualitative interview period. Each participant will be in the study for a total of up to 17 weeks (i.e., including maximum allowable time-windows for assessments).

[figure not shown]
There will be virtual visits (i.e., audio or video calls between participant and researcher) at screening, on first intervention day, for optional qualitative interview, and to provide support with additional intervention sessions or assist the participant (e.g., with outcome completion) when appropriate. Remote participant assessments (i.e., typically without researcher; online questionnaires only) will take place at Baseline, 4 and 8 weeks.

The study will enrol up to approximately 150 participants, 75 participants per study arm. This study may conclude early i.e., before reaching the max 150 participants (Please refer to *P1V GAINS IN01 Optimisation SAP* for details on early stopping of the trial). Total duration of the study from first participant enrolment to last participant

completing the study is expected to last approximately 9 months but will depend on the number enrolled.

Please see study flow chart below representing the overall trial design:

**Figure 1: STUDY FLOW CHART**

## 2.2 Randomisation & Blinding

### 2.2.1 Randomisation

Participants who meet the eligibility criterion of having 3 or more intrusive memories in the run-in week will be allocated to either the immediate intervention arm or the delayed intervention arm using a 1:1 overall ratio. Participants will have a 85% chance of being allocated to the arm with the fewest participants, to minimise the difference in group sizes between the two arms. This approach leads to relatively balanced groups sizes, even with small samples (Hagino et al., (2004)). The randomisation program will be incorporated into P1vital® ePRO (a secure web-based clinical research system) to ensure that allocation cannot be influenced by the research team (i.e. randomisation is computerised and automated to ensure allocation concealment).

After randomisation, the study researcher will not tell the participant which study arm they are assigned.

### 2.2.2 Blinding

Statisticians will be blinded to allocation, and all assessments are self-report questions administered digitally, eliminating assessor bias (i.e., to ensure blinding of outcome assessment). As all eligible participants are randomised to receive the intervention, but at two different time points, all will be told that they will receive the intervention and have access to it for 4 weeks at some point over the next 8 weeks. They will also all be informed that they will be asked to complete an online daily intrusive memory diary for some of those weeks. Researchers involved in contacting the participants and facilitating the conduct of intervention will not be blinded: however, as both arms receive the same intervention but at different time points (and the same clinicians will be administering the intervention in both arms), clinician motivation is likely to be unbiased (thereby minimising performance bias on part of the clinician). The remaining principal investigator's delegated study members will also be unblinded during the length of the trial.

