**Study Period:**

Each participant will be in the study for a total of up to 17 weeks. There will be virtual visits (i.e., audio or video calls between participant and researcher) at screening, on first intervention day, for optional qualitative interview, and to provide support with additional intervention sessions or assist the participant (e.g., with outcome completion) when appropriate. Remote participant assessments (i.e., typically without researcher; online questionnaires only) will take place at Baseline, 4 and 8 weeks.

Total duration of the study from first participant enrolment to last participant completing the study is expected to last approximately 9 months, but will depend on the number enrolled.

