**Outline of Study:**

The study is divided into approximately a 1-5 week screening period including one week run-in period to determine eligibility prior to randomisation followed by approximately 8 weeks in the study period and 2 weeks optional, qualitative interview period.

Participants will be recruited through the Intensive Care Society network membership and existing social media followers supplemented by targeted advertisements in social media (e.g. Facebook, Twitter).

Those who are interested in taking part in the study will be asked to complete a brief online eligibility questionnaire anonymously, which can be accessed on the study website. Participants will be asked to give online consent before completing the questionnaire. Those who meet all the inclusion criteria will be asked to provide their contact details (name, telephone number and email address). A researcher will then arrange a time to contact them by phone or video call to obtain informed consent and go through the study inclusion and exclusion criteria.

All participants will be asked to complete a daily online intrusive memory diary for a run-in period of one week to record a simple count of the number of intrusive memories they have each day using a secure web-based clinical research system, P1vital® electronic patient reported outcome (ePRO) system. Those meeting the study eligibility criteria will then be sent a link to complete baseline questionnaires using ePRO. After completing baseline questionnaires, participants will be randomised by ePRO to receive either the immediate intervention arm or the delayed intervention arm using a 1:1 overall ratio. After randomisation, participants will be sent information explaining what will happen next in the study. This information will differ according to whether they have been allocated to the immediate intervention or delayed intervention arm. Note: to minimise expectation bias, participants are not told that the study has two arms or to which arm they have been assigned; participants are informed during the consent process that they will have access to an online intervention for 4 weeks 'at some point' within an 8-week period.

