## 5.6 Intervention procedures

After completing baseline questionnaires, participants will be sent information explaining what will happen next in the study. This information will differ according to whether they have been allocated to the immediate intervention or delayed intervention arm. Participants in the immediate intervention arm will be contacted to arrange a time to go through the digital intervention instructions with them for the first time (see below). They will then have access to the digital intervention for 4 weeks. Participants in the delayed intervention arm will be asked to complete the online intrusive memory diary and intrusive memory ratings using ePRO (as for the run-in week, section 5.4), at week 4. They will then be contacted by a researcher to arrange a time to go through the digital intervention instructions with them (as in the immediate intervention group). They will have access to the digital intervention for the next 4 weeks.

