### 7.1.2 Blinding of Study Intervention

Statisticians will be blinded to allocation, and all assessments are self-report questionnaires administered digitally, eliminating assessor bias (i.e., to ensure blinding of outcome assessment). As all eligible participants are randomised to receive the intervention, but at two different time points, all will be told that they will receive the intervention and have access to it for 4 weeks at some point over the next 8 weeks. They will also all be informed that they will be asked to complete an online daily intrusive memory diary for some of those weeks. Researchers involved in contacting the participants and facilitating the conduct of intervention will not be blinded: however, as both arms receive the same intervention but at different time points (and the same clinicians will be administering the intervention in both arms), clinician motivation is likely to be unbiased (thereby minimising performance bias on part of the clinician). The remaining principal investigator's delegated study members will also be unblinded during the length of the trial.

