## **9.0 Primary and Secondary Endpoints**

### **9.1 Primary Endpoint**

- Number of intrusive memories of traumatic events recorded by participants in a brief daily online intrusive memory diary for 7 days during week 4 (i.e. from Day 22 to 28 post first intervention session in immediate intervention arm/equivalent timeframe in delayed intervention arm). Analysed as between-group comparison (immediate intervention arm vs. the delayed intervention arm) controlling for the number of intrusive memories during the run-in week.

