## **10.0 Data Handling**

### **10.1 Source Data Collection**

Source documents are original documents, data and records. These include, but are not limited to, study related documents e.g. Informed consent form, ePRO questionnaire data, i-spero® intervention data, Adverse events.

The following data will be recorded in the study file (paper source):

- Participant information sheet
- Eligibility Questionnaire
- Consent form
- Contact details
- Inclusion/Exclusion Criteria
- Intrusive memory daily and weekly data (missed during electronic source entry)

The following data will be recorded directly into the ePRO system by participant (electronic source):

- Intrusive memory diary (daily)
- Intrusive memory rating (end of week)
- Randomisation
- Credibility/Expectancy Questionnaire
- Demographics
- Health background
- Checklist of traumatic events
- Perceived threat to self/other
- Peritraumatic Distress Inventory
- Support from managers and from family/friends
- Impact of Event scale-Revised (IES-R)
- PTSD Checklist for DSM-5 (PCL-5)
- Generalised Anxiety Disorder (GAD-2)

- Patient Health Questionnaire (PHQ-2)
- Sleep Condition Indicator
- Psychological Outcome Profiles Questionnaire (PSYCHLOPS)
- World Health Organisation Disability Assessment Schedule (WHODAS) 2.0
- EQ-5D-5L (5-LEVEL EuroQol 5D)
- Sickness absence
- Scale of Work Engagement and Burnout (SWEBO)
- Intention To Leave Job
- Changes to health and work

The following intervention data will be recorded directly into the i-spero® system (electronic source).

- Intervention: List of intrusive memories (hotspots)
- Intervention: Distress rating (x3)
- Intervention: Reactivation vividness rating
- Intervention: Mental rotation rating
- Intervention: Record of intrusive memories (daily)
- Feedback Questionnaire

The following data will be recorded directly on audio files and stored in the study file (electronic source).

- Qualitative interviews

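### Digital self-report does not blind outcome assessment: participants know whether they have had the intervention, and the documents allow outcome data that are assisted or captured outside ePRO

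*SAP*

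**What the plan says.** SAP 2.2.2 states that "all assessments are self-report questions administered digitally, eliminating assessor bias (i.e., to ensure blinding of outcome assessment". Protocol 7.1.2 makes the same claim: "all assessments are self-report questionnaires administered digitally, eliminating assessor bias (i.e., to ensure blinding of outcome assessment".

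Protocol 9.1 defines the primary endpoint as "Number of intrusive memories of traumatic events recorded by participants in a brief daily online intrusive memory diary for 7 days during week 4". On what participants know about the eight weeks ahead, SAP 2.2.2 says that "all will be told that they will receive the intervention and have access to it for 4 weeks at some point". The Protocol Synopsis (Outline of Study) adds that "participants are not told that the study has two arms or to which arm they have been assigned", and gives the reduction of expectation bias as the reason. Protocol 5.6 says of the material sent out next: "This information will differ according to whether they have been allocated to the immediate intervention or delayed intervention arm".

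Two further provisions concern how outcome data may arise. Under Study Period, the Protocol Synopsis allows virtual visits "to provide support with additional intervention sessions or assist the participant (e.g., with outcome completion) when appropriate"; SAP 2.1 repeats this and adds that the remote assessments are typically done without a researcher. Protocol 10.1 lists among the paper source data: "Intrusive memory daily and weekly data (missed during electronic source entry". That list is separate from the list of data the participant enters directly into ePRO.

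On staff, both blinding sections say that statisticians are blinded, while the researchers who contact participants and facilitate the intervention, and the remaining delegated study members, are not.

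**The concern.** For a self-reported count the person who reports is the assessor. Whether assessment is blinded therefore depends on what that person knows. Removing a separate rater does not settle it. If participants know that they have, or have not yet, had the intervention that everyone was promised, their counts can reflect expectation or waiting as well as the frequency of intrusive memories.

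The claim also rests on every assessment being digital self-report. If some diary counts or questionnaires are completed with an unblinded researcher on a call, or captured outside ePRO, that premise is not fully met.

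At stake is what the report may conclude. A report that follows the present text would describe the primary outcome as assessed blind and free of assessor bias, and readers would make no allowance for reporting differences between arms. The same outcome also informs the interim decisions on modifying the intervention and stopping early (Protocol 3.2, SAP 2.5).

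**Working it through.** The claim rests on no stated figure, so the check is mainly a reading of the sections against one another. One piece of arithmetic bears on the share of missed diary days.

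**1. Who assesses the primary outcome.** Protocol 9.1 and SAP 5.1.1: the participant, by daily diary over Days 22 to 28.

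**2. What that person knows by Day 22.**
- Immediate arm (Protocol 5.7.1, 5.7.2): a virtual visit on Day 1 to complete the intervention with a researcher, then continuous access and a daily record of intrusive memories in i-spero. Repeat use is optional (Protocol 5.6.1), but the guided session alone makes receipt plain.
- Delayed arm (Protocol 5.7.1, 5.7.2): nothing to complete in weeks 1 to 3.
- Both arms: told in advance to expect four weeks of access at some point within eight.

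A participant can therefore tell whether the intervention has been received, even without knowing that a second arm exists. Withholding the two-arm design hides the comparison, not receipt.

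**3. Whether every assessment is unaided digital self-report.**
- Assisted completion is allowed (Protocol Synopsis, Study Period; SAP 2.1). Unassisted completion is described as typical, not universal.
- Missed diary data are placed in the study file, apart from direct ePRO entry (Protocol 10.1).
- Study members other than the statisticians are unblinded (Protocol 7.1.2, SAP 2.2.2).

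Both provisions sit outside the description in the blinding sections.

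**4. How much diary data could be affected by the second route.** Inputs: up to about 75 participants per arm (Protocol Synopsis); 7 diary days in week 4; 99.4% completion in a pilot of this type of diary with NHS staff (Protocol 5.4.1).
- Diary days per arm: 75 × 7 = 525.
- Missed days at the pilot rate: 525 × (1 − 0.994) = 525 × 0.006 = 3.15, or about 3 per arm.

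This assumes full enrolment and that the pilot rate carries over. Even if every missed day were recovered outside ePRO, the share would be about 0.6%. The calculation does not cover calls in which a participant is helped to make an ePRO entry; the documents give no number for those.

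**5. Whether the analysis would show it.** SAP 5.2.3 has three sensitivity analyses: observed data only, observation-level random effects, and exclusion of outliers. SAP 5.3 covers imputation. None separates counts by how they were obtained, so a recovered or assisted count would enter as ordinary observed data.

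**The case against.** The strongest reply is that the plan does protect against bias, and that participants' awareness of receipt cannot be avoided in a delayed-access behavioural trial. Participants are not told that a comparison exists, and researchers do not tell them their arm. Assessments are usually completed alone, which does remove a rater's influence. Statisticians are blinded. The trial is an optimisation study meant to inform a later definitive one, and no model or threshold depends on the blinding sentence. All of this stands. It shows that the design is reasonable, but not that the sentence is right. Reducing expectation bias is a more modest aim than eliminating assessor bias, and unavoidable awareness should be stated as such.

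A reader might go further and infer that the design offers no protection at all. The documents do not support that, for the reasons just given.

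A reader might also infer that unblinded staff collect missed counts from participants. Protocol 10.1 does not say who supplies or records those data. Its paper-source label is not strictly literal either: the same list holds the eligibility questionnaire, completed online (Protocol 5.2), and the consent form, signed electronically by email (Protocol 5.3). What can be said is that missed diary data are handled apart from direct ePRO entry by a route the documents do not describe.

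Finally, the baseline Credibility/Expectancy score might seem to offer a test for the bias. It is collected before randomisation, so it cannot capture expectations that diverge once one arm has had the intervention. An arm-by-expectancy interaction could also be genuine effect modification, and a null result would not exclude reporting bias.

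**Conclusion.** The claim of blinded outcome assessment in Protocol 7.1.2 and SAP 2.2.2 is wrong as written and should be corrected. The primary count is reported by a participant who knows whether the intervention has been received. The accompanying statement that all assessments are digital self-report is not consistent with Protocol 10.1 or with the provision for assisted completion. The design itself can stand.

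On size, two parts must be kept apart. The documents give no basis for the amount by which awareness of receipt might change self-reports, and no figure is offered here. Diary days missed in ePRO are probably few: about 3 of 525 per arm if the pilot completion rate holds. The number of assisted completions is unknown. The main point does not depend on either count; it follows from who reports the outcome and what that person knows.

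**What to change.** - **Wording, Protocol 7.1.2 and SAP 2.2.2.** Replace the claim with a statement that outcomes are participant-reported; that participants are masked to the two-arm design but not to receipt of the intervention; that outcome assessment is therefore not blinded; and that conclusions will be worded accordingly. The blinding of statisticians can stay as stated.
- **Source of the data.** State who may record missed diary data and how. Flag every diary count or questionnaire completed with researcher help or outside ePRO, and report the numbers by arm.
- **SAP 5.2.3.** Add a rerun of the primary model with the flagged diary counts set to missing and handled as in SAP 5.3.
- **Optional.** An ePRO prompt, identical in both arms, for participants to enter missed days themselves. It would bring some recall into a daily diary, so it is a choice and not a requirement.

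The cost is two text changes, one source flag, a short table by arm and one extra model run. If collection is already under way, the flag would have to be compiled from the study file. The report gives up a favourable blinding statement. Treatment, endpoint and sample size do not change.
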